10.4 Appendix 4: Contraceptive guidance and collection of pregnancy information

10.4.1 Definitions

10.4.1.1 Woman of childbearing potential

In general, a woman is considered fertile following menarche and until becoming post-menopausal unless permanently sterile (see below).

In this study, the only women considered to be of non-childbearing potential who are eligible for inclusion are:

1. Premenopausal females with 1 of the following:

- Documented hysterectomy
- Documented bilateral salpingectomy

Note: Documentation can come from the site personnel's review of the participant's medical records, medical examination, or medical history interview.

10.4.2 Contraception guidance

10.4.2.1 Male participants

Not applicable.

10.4.2.2 Pregnancy testing

- WOCBP should only be included after a confirmed menstrual period and a negative highly sensitive serum pregnancy test.
- Pregnancy testing will be performed whenever a menstrual cycle is missed or when pregnancy is otherwise suspected.
- Serum beta human chorionic gonadotropin (HCG) pregnancy testing will be performed at all timepoints mentioned in the Schedule of activities.
- The result must be negative prior to dosing the study participant.

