1.3.1.2 Part 1 Sequence B

Table 1-5: Schedule of activities- Part 1 Treatment Sequence B

Day	Screening	Baseline	OC			Washout (14 Days)	PSL+OC						EOS/ SFU EDV ^a						
			1	2	3		18	19 to 20	21 to 22	23 to 29	30	31		32 to 33	34 to 35	36			
Written informed consent	X	-1																	
Demographics and baseline characteristics	X																		
Inclusion /Exclusion criteria verification	X	X	X				X												
General medical /medications/ procedures history	X	X					X (D17)												
Suicidality Risk Assessment (C-SSRS) ^b	X	X					X (D17)												X
Psychiatric and mental status evaluation	X	X						X	X	X	X	X	X	X	X	X	X	X	X
Physical examination ^c	X	X						X	X	X	X	X	X	X	X	X	X	X	X
Vital signs ^d	X	X						X	X	X	X	X	X	X	X	X	X	X	X
Pregnancy test	X	X						X (D17)											
Hematology, clinical chemistry, urinalysis	X	X					X (D17)												X
Serology (HIV, HbsAg, HEV, syphilis, and HCV-Ab)	X	X																	
12-lead ECG	X	X	X					X	X ^e	X ^e	X ^e	X ^e	X ^e	X ^e	X ^e	X ^e	X ^e	X ^e	X

Table 1-5: Schedule of activities- Part 1 Treatment Sequence B

	Screening	Baseline	OC			Washout (14 Days)	PSL+OC						EOS/ SFU EDV ^a		
			1	2	3		18	19 to 20	21 to 22	23 to 29	30 31	32 to 33		34 to 35	36
Day	-29 to -2	-1	1	2	3	4 to 17	18	19 to 20	21 to 22	23 to 29	30 31	32 to 33	34 to 35	36	43 to 46
Urine and cotinine drug screen, and alcohol breath test	X	X				X (D17)									
Recording of adverse events/medical procedures	X	X	X	X	X	X(D17)	X	X	X	X	X	X	X	X	X
Blood sampling for genotyping of drug metabolizing enzymes and/or transporters															
Admit to clinic		X				X(D17)									
Administer PSL							X	X	X	X	X	X	X	X	
Administer OC			X							X					
Blood sampling for PSL PK levels								X ^f	X ^f	X ^f	X ^f	X ^f			
Blood sampling for OC PK levels			X ^g	X ^g	X ^g					X ^g	X ^g	X ^g			
Blood sampling for cross-validation ^h										X					
Discharge					X										X (D37 or D38) ^j

C-SSRS=Columbia Suicide Severity Rating Scale; ECG=electrocardiogram; EDV= Early Discontinuation Visit; EOS=End of Study; h=hour(s); HbsAg-Ab=HepB surface antigen antibodies; HCV-Ab=HepC virus antibodies; HEV=hepatitis E virus; HIV=human immunodeficiency virus; OC=oral contraceptive; PK=pharmacokinetic; PSL=padsevonil; SFU=Safety Follow-Up

^a If a study participant discontinues early, SFU procedures should be completed as the EDV. Upon early termination/withdrawal, the study participant will be encouraged to complete SFU assessments following the last dose of study medication.

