- b All study participants will complete the "Screening/Baseline" version of the C-SSRS during Screening (assessing the past 6 months), followed by the "Since Last Visit" version at subsequent visits.
- c At Screening, Baseline (Day -1), Day 23, and Day 29, a full physical examination will be performed. On all other days a physical examination is performed, it will be a brief physical examination (Section 8.3.1). On days 24-28, physical examination will not be performed.
- d Oral or aural body temperature must be performed using the same method in any individual study participant on all occasions.), pulse rate, respiratory rate, and blood pressure will be assessed. Vital signs (to be taken before blood collection for laboratory tests) will consist of 1 pulse and 1 blood pressure measurement.
- e ECG will be completed on Days 19, 21, 23, and 29 only of multiple day periods during Treatment Sequence B.
- f During the OC+PSL Treatment Period, trough levels of PSL will be collected on morning before PSL dosing on Day 19, Day 21, Day 23, Day 25, and Day 27. Additional blood sampling for PK analysis will be taken on Day 29 (PSL PK) before (predose) and after PSL morning dose at 0.25h, 0.5h, 1h, 1.5h, 2h, 3h, 4h, 6h, 8h, 12h postdose and on Day 30 (PSL PK) before (predose) and after the PSL and OC morning dose at 0.25h, 0.5h, 1h, 1.5h, 2h, 3h, 4h, 6h, 8h, 12h postdose. In addition, blood samples will be obtained prior to the morning dose on Day 31 and prior to the morning dose on Day 32.
- g During the single-dose OC period, PK blood samples will be taken on Day 1 at predose and 0.25h, 0.5h, 1h, 1.5h, 2h, 3h, 4h, 6h, 8h, 12h, 24h (Day2), 36h (Day 2), and 48h (Day 3) postdose. During OC+PSL Treatment Period, blood sampling for OC PK analysis will be taken on Day 30 (before OC+PSL morning dose) and after PSL and OC morning dose at 0.25h, 0.5h, 1h, 1.5h, 2h, 3h, 4h, 6h, 8h, 12h, 24h (Day 31), 36h (Day 31), and 48h (Day 32) postdose.
- h Mitra™ (finger prick) blood samples will be taken at 0.5h, 1h, 3h, 6h, 12h postdose on Day 29 only. See Section 8.1.1 for details about selection.
- i The study participant can be discharged on Day 37 or Day 38, at the discretion of the principal investigator.

1.3.2 Part 2

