- ^c At Screening, Baseline (Day -1), and Day 25, a full physical examination will be performed. On all other days a physical examination is performed, it will be a brief physical examination (Section 8.3.1). On Days 19-24, physical examination will not be performed.
- ^d Oral or aural body temperature (temperature must be performed using the same method in any individual study participant on all occasions.), pulse rate, respiratory rate, and blood pressure will be assessed. Vital signs (to be taken before blood collection for laboratory tests) will consist of 1 pulse and 1 blood pressure measurement.
- ^e ECG will be completed on Days 19, and 25 only of multiple day periods during Treatment Sequence B.
- ^f Psychiatric and mental evaluation will be done pre-dose.
- ^g During the OC+PSL Treatment Period, trough levels of PSL will be collected on morning before PSL dosing on Day 19, Day 21, and Day 23. Additional blood sampling for PK analysis will be taken on Day 25 before (predose) and after PSL morning dose at 0.25h, 0.5h, 1h, 1.5h, 2h, 3h, 4h, 6h, 8h, 12h postdose and on Day 26 before (predose) and after the PSL and OC morning dose at 0.25h, 0.5h, 1h, 1.5h, 2h, 3h, 4h, 6h, 8h, 12h, 24h (Day 27), and 48h (Day 28) postdose.
- ^h During the single-dose OC period, PK blood samples will be taken on Day 1 at predose and 0.25h, 0.5h, 1h, 1.5h, 2h, 3h, 4h, 6h, 8h, 12h, 24h (Day 2), 36h (Day 2), and 48h (Day 3) postdose. During OC+PSL Treatment Period, blood sampling for OC PK analysis will be taken on Day 26 (before OC+PSL morning dose) and after PSL and OC morning dose at 0.25h, 0.5h, 1h, 1.5h, 2h, 3h, 4h, 6h, 8h, 12h, 24h (Day 27), 36h (Day 27), and 48h (Day 28) postdose.
- ⁱ The study participant can be discharged on Day 29 or Day 30, at the discretion of the principal investigator.
- ^j Mitra™ (finger prick) and venous blood samples will be taken at 0.5h, 1h, 3h, 6h, 12h postdose on Day 25 only for selected study participants. See Section 8.1.1 for details about selection.

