4 STUDY DESIGN

4.1 Overall design

This is a Phase 1, open label, randomized, two-way cross-over study to investigate the potential PK interaction of PSL with OC in healthy female study participants. The designs of Part 1 and Part 2 are shown in Table 1-2 and Table 1-3.

A study participant who provides written informed consent will be screened within 28 days before the first Treatment Period. Each Part of the study (Part 1 and Part 2) consists of a Screening Period, 2 Treatment Periods, a Washout Period, and a Safety-Follow-Up (SFU) Period of 7 to 10 days (Part 1) or 7 to 14 days (Part 2).

Study participants who meet all inclusion criteria and none of the exclusion criteria will check into the clinic the day prior to the first day of the first Treatment Period and will be randomized into one of the treatment sequences: Treatment Sequence A or Treatment Sequence B.

The Treatment Periods will consist of a single dose of OC or a dose of OC combined with multiple doses of PSL for a time period. The OC Treatment Periods are separated by a Washout Period lasting at least 14 days.

Part 1

Sequence A

In Part 1, study participants enrolled in Treatment Sequence A will be administered PSL BID (up-titration to steady-state [400mg BID]) from Day 1 to Day 5, followed by a steady-state period from Day 6 to Day 12 with a single dose of OC administered on the morning of Day 13. A taper of PSL will occur from Day 15 to Day 19. Starting on Day 20, the study participants will then complete a Washout Period for 14 days followed by a return to the clinic for the OC-only dosing on Day 34. Pharmacokinetic samples will be collected on the days shown in Table 1-2,

Treatment Sequence A. An SFU Visit will occur between Day 41 and Day 44. All assessments, including PK sampling, are shown in the Schedule of Activities (Part 1, Treatment Sequence A, Table 1-4).

Sequence B

Study participants enrolled in Treatment Sequence B will be administered a single dose of OC on the morning of Day 1 followed by PK assessments that day and the next 2 days. The study participants will then complete a 14-day Washout Period followed by a return to the clinic for the OC+PSL dosing from Day 18 to Day 36 (OC to be administered on Day 30).

Pharmacokinetic samples will be collected on the days shown in Table 1-2,

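### No pregnancy test is scheduled at EOS/SFU/EDV, so Sequence B participants and anyone withdrawn on padsevonil have no scheduled check after exposure

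*Protocol*

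**What the plan says.** Protocol Section 10.4.2.2 makes the schedules the only source of planned tests: "Serum beta human chorionic gonadotropin (HCG) pregnancy testing will be performed at all timepoints mentioned in the Schedule of activities". In Protocol Tables 1-4 to 1-7 the row headed "Pregnancy test" is marked at Screening, at Day -1 and on one re-admission day: Day 33 (Part 1 Sequence A), Day 25 (Part 2 Sequence A) or Day 17 (Sequence B in both parts). The EOS/SFU/EDV cell is blank in every table. SAP Tables 2-4 to 2-7 repeat the same pattern.

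In Sequence B the washout is spent out of the clinic, "followed by a return to the clinic for the OC+PSL dosing from Day 18 to Day 36" in Part 1 (Day 18 to Day 28 in Part 2). Re-admission is on Day 17, and participants then stay in the unit until after the last PSL dose. In Part 1, "The study participant can be discharged on Day 37 or Day 38, at the discretion of the principal investigator"; in Part 2, "The study participant can be discharged on Day 29 or Day 30, at the discretion of the principal investigator".

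For withdrawals, footnote a to each schedule says: "If a study participant discontinues early, SFU procedures should be completed as the EDV".

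Section 10.4.2.2 has two backstops. One is testing for cause: "Pregnancy testing will be performed whenever a menstrual cycle is missed or when pregnancy is otherwise suspected". The other applies at entry: "WOCBP should only be included after a confirmed menstrual period and a negative highly sensitive serum pregnancy test". It also requires a negative result before dosing.

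**The concern.** The two sequences are protected unequally, and no reason is given. A Sequence A completer is tested after PSL, at re-admission for the OC-only period. A Sequence B completer is last tested the day before PSL begins and is never scheduled for another test.

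Conception during PSL dosing itself is very unlikely in Sequence B, because participants are resident. The realistic route is a conception in the outpatient washout that is too recent to show on Day 17. It passes the negative-before-dosing rule and is then exposed to the full PSL course. Sequence A has the same blind spot just before Day -1, but its later test closes it for completers.

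Participants withdrawn on PSL, in either sequence, complete the SFU procedures as their EDV, and those contain no pregnancy test. Such withdrawals are foreseeable: the rationale for Amendment 2 gives reducing them as one of its aims.

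What is at stake is detection. Pregnancy follow-up under Section 8.4.5 starts only once a pregnancy is known. Without a closing test, an exposed pregnancy would come to light only through a missed cycle, suspicion or self-report.

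**Working it through.** There is no planned figure to reproduce here. The check compares the test days with the dosing and visit days.

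**Schedules side by side** (Protocol Tables 1-2 to 1-7)

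| Schedule | Last scheduled test | PSL days | Last test relative to PSL | SFU window |
|---|---|---|---|---|
| Part 1 Sequence A | Day 33 | 1 to 19 | 33 − 19 = 14 days after last dose | 41 to 44 |
| Part 1 Sequence B | Day 17 | 18 to 36 | 1 day before first dose | 43 to 46 |
| Part 2 Sequence A | Day 25 | 1 to 11 | 25 − 11 = 14 days after last dose | 33 to 40 |
| Part 2 Sequence B | Day 17 | 18 to 28 | 1 day before first dose | 35 to 42 |

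PSL days after a falsely negative Day 17 test: 36 − 18 + 1 = 19 in Part 1 and 28 − 18 + 1 = 11 in Part 2.

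**What Day 17 can miss in Sequence B.** The washout is Days 4 to 17, which is 14 days. The documents do not say how long after conception serum hCG turns positive, so the lag is an assumption. The main range is 10 to 14 days, with shorter values shown for comparison. The latest detectable conception day is 17 minus the lag.

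| Assumed lag (days) | Latest conception detected on Day 17 | Washout days missed |
|---|---|---|
| 7 | 17 − 7 = Day 10 | Days 11 to 17 = 7 |
| 10 | 17 − 10 = Day 7 | Days 8 to 17 = 10 |
| 12 | 17 − 12 = Day 5 | Days 6 to 17 = 12 |
| 14 | 17 − 14 = Day 3 | Days 4 to 17 = 14 |

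**What an SFU test would recover.** Take the least favourable case, the earliest visit with the longest lag. Part 1 reaches back to 43 − 14 = Day 29, and Part 2 to 35 − 14 = Day 21. Both are later than Day 17, so every washout conception missed on Day 17 would be detected.

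**Sequence A completers.** With a 14-day lag the existing tests reach back to 33 − 14 = Day 19 and 25 − 14 = Day 11. A conception before admission on Day -1 is therefore found.

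**Early withdrawals.** For an EDV test to cover every conception before admission, it must fall at least one lag after admission. With a lag of 10 to 14 days this means Day 17 + 10 = Day 27 to Day 17 + 14 = Day 31 in Sequence B. In Sequence A, counting Day -1 as zero, it means about Day 10 to Day 14. An earlier EDV gives partial coverage only.

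**The case against.** The strongest counter-argument is that an existing mandatory rule should act sooner than the proposed test. If menses are due about 14 days after conception (an assumption), conceptions on Days 4 to 17 would produce a missed period on about Days 18 to 31. In Part 1 that falls wholly within residence, about 12 days or more before the earliest SFU visit (43 − 31 = 12). In Part 2 it falls mostly within residence and still before SFU. Appendix 2 also allows additional tests at the investigator's discretion, and the Day 17 medical history gives an opportunity to ask about menses.

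The risk is also very small. Table 10-1 prints a failure rate below 1% per year. It stands under the user-dependent heading; suppose it applies to the permitted methods. Over 14 days this is 0.01 × 14/365, or about 0.04% per woman. For the 7 Part 1 Sequence B completers the expected number of pregnancies is about 7 × 0.00038 = 0.003.

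Other points are that the test prevents no exposure, that it would not reliably cover conceptions after discharge, and that SAP Section 4.4 asks withdrawers to return as soon as possible, so an early EDV test could be falsely reassuring. The study has also stopped.

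Most of this stands, and it is why the point is minor. It does not close the gap. The missed-cycle rule depends on someone recognising a late period. These women have taken single OC doses, no schedule row records menses, and the confirmed menstrual period is required for inclusion, before the washout. Eligibility is re-verified on Day 18 in Sequence B, but that row does not name menses either. Contraception lowers the chance of pregnancy but does not detect a failure. A shorter hCG lag narrows the gap, but at 7 days half of the washout is still undetected.

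**Conclusion.** The concern holds as a low-priority participant-safety improvement. All eight tables leave EOS/SFU/EDV blank. Sequence B therefore has no scheduled test once PSL has started, and nor does anyone withdrawn on PSL. Under the assumed lag of 10 to 14 days, the Day 17 test cannot see conceptions on 10 to 14 of the 14 washout days, and an SFU test would detect all of them in both parts.

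The number of affected women cannot be given, because the documents state neither how many participants were of childbearing potential nor how many were withdrawn on PSL. It is likely to be very small: highly effective non-hormonal contraception is required of women of childbearing potential, and some participants may not be able to conceive. The primary PK analysis and the sample size are untouched. SAP Section 1 records that the study has stopped and that nobody will enter Part 2, so the recommendation applies to the protocol as written or to its reuse.

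**What to change.** Mark a serum hCG test for women of childbearing potential in the EOS/SFU/EDV column of Protocol Tables 1-4 to 1-7 and of SAP Tables 2-4 to 2-7. Section 10.4.2.2 then makes it mandatory without further text.

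The cost is one extra assay per woman of childbearing potential. Hematology and clinical chemistry are already drawn at that visit in all four protocol schedules, so no new visit or venepuncture is needed.

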10.4.2.3 Collection of pregnancy information

10.4.2.3.1 Female participants

Female participants of childbearing potential are eligible to participate if they agree to use a highly effective method of contraception consistently and correctly as described in [Table 10-1](#).

Table 10-1: Highly Effective Contraceptive Methods

Highly Effective Contraceptive Methods That Are User Dependent^a
 
Failure rate of <1% per year when used consistently and correctly.
 
 • Combined (estrogen and progestogen containing) hormonal contraception and progesterone only hormonal contraceptive methods are not permitted in this study.

Highly Effective Methods That Are User Independent
 
 • Intrauterine device (IUD) • Bilateral tubal occlusion • Vasectomized partner 
A vasectomized partner is a highly effective contraception method provided that the partner is the sole male sexual partner of the WOCBP and the absence of sperm has been confirmed. If not, an additional highly effective method of contraception should be used.
 
 • Sexual abstinence 
Sexual abstinence is considered a highly effective method only if defined as refraining from heterosexual intercourse during the entire period of risk associated with the study medication. The reliability of sexual abstinence needs to be evaluated in relation to the duration of the study and the preferred and usual lifestyle of the participant.

^a Typical use failure rates may differ from those when used consistently and correctly. Use should be consistent with local regulations regarding the use of contraceptive methods for participants in clinical studies.

10.4.2.3.2 Male participants with partners who become pregnant

Not applicable.

10.4.2.3.3 Female participants who become pregnant

- The Investigator will collect pregnancy information on any female participant who becomes pregnant while participating in this study. Information will be recorded on the appropriate form and submitted to the Sponsor within 24 hours of learning of a participant's pregnancy. The participant will be followed to determine the outcome of the pregnancy. The Investigator will collect follow-up information on the participant and the neonate and the information will be forwarded to the Sponsor. Generally, the follow-up will be at least 30 days (or up to 12 months) after the delivery date. Any termination of pregnancy will be reported, regardless of fetal status (presence or absence of anomalies) or indication for the procedure.
- While pregnancy itself is not considered to be an AE or SAE, any pregnancy complication or elective termination of a pregnancy will be reported as an AE or SAE. A spontaneous abortion is always considered to be an SAE and will be reported as such. Any post-study pregnancy-related SAE considered reasonably related to the study medication by the Investigator will be reported to the Sponsor as described in Section 8.4.5. While the Investigator is not obligated to actively seek this information in former study participants, he or she may learn of an SAE through spontaneous reporting.
- Any female participant who becomes pregnant while participating in the study will be withdrawn from the study.

10.5 Appendix 5: Genetics

Genetics are not evaluated in this study; however, a blood sample will be taken for potential genotyping of metabolizing enzymes and/or drug transporters. Genotyping samples will be destroyed once the clinical study report has been finalized, approximately 1 year after the end of the study.

This document cannot be used to support any marketing authorization application and any extensions or variations thereof.

REDACTED COPY

10.6 Appendix 6: Liver safety—suggested actions and follow-up assessments

Participants with PDILI must be assessed to determine if study medication must be discontinued. In addition, all concomitant medications and herbal supplements that are not medically necessary should be discontinued.

Investigators should attempt to obtain information on study participants in the case of study medication discontinuation to complete a final evaluation.

Study participants with PDILI should not be withdrawn from the study until investigation and monitoring are complete. All results of these evaluations and observations, as well as the reason(s) for study medication discontinuation and/or participant withdrawal (if applicable), must be recorded in the source documents. The eCRF must document the primary reason for discontinuation of study medication.

A specific monitoring plan must be agreed between the UCB Study Physician and the Investigator for study participants who have ALT >5 ULN. The monitoring plan should include any necessary follow-up assessments (until resolution of the abnormal lab values).

Phase 1 liver chemistry stopping criteria are designed to assure participant safety and to evaluate liver event etiology ([Table 10-2](#)).

Table 10-2: Phase I liver chemistry stopping criteria and follow-up assessments

Liver Chemistry Stopping Criteria – Liver Stopping Event	
ALT-absolute	
ALT \geq 3xULN
 
If ALT \geq 3xULN AND bilirubin \geq 2xULN (>35% direct bilirubin) OR international normalized ratio (INR) > 1.5, report as a serious adverse event (SAE).^{a,b}
 
See additional actions and follow-up assessments listed below.

Suggested Actions and Follow-up Assessments	
Actions	Follow-Up Assessments

This document cannot be used to support any marketing authorization application and any extensions or variations thereof.

REDACTED COPY


 • Report the event to the UCB within 24 hours. • Complete the liver event eCRF, and complete an SAE data collection tool if the event also met the criteria for an SAE.^b • Perform liver chemistry follow-up assessments. • Monitor the participant until liver chemistry test abnormalities resolve, stabilize, or return to baseline (see MONITORING). 
MONITORING:
 
If ALT $\geq 3xULN$ AND bilirubin $\geq 2xULN$ or INR >1.5:
 
 • Repeat liver chemistry tests (include ALT, aspartate transaminase [AST], alkaline phosphatase, bilirubin) and perform liver event follow-up assessments within 24 hours. • Monitor participant twice weekly until liver chemistry test abnormalities resolve, stabilize, or return to baseline. • A specialist or hepatology consultation is recommended. 
If ALT $\geq 3xULN$ AND bilirubin $< 2xULN$ and INR ≤ 1.5:
 
 • Repeat liver chemistry tests (include ALT, AST, alkaline phosphatase, bilirubin) and perform liver chemistry follow-up assessments within 24 to 72 hours. • Monitor participants weekly until liver chemistry abnormalities resolve, stabilize, or return to baseline. 	
 • Viral hepatitis serology.^c • Obtain INR and recheck with each liver chemistry assessment until the transaminases values show downward trend. • Serum creatine phosphokinase (CPK) and lactate dehydrogenase (LDH). • Fractionate bilirubin, if total bilirubin $\geq 2xULN$. • Obtain complete blood count with differential to assess eosinophilia. • Record the appearance or worsening of clinical symptoms of liver injury or hypersensitivity on the AE eCRF. • Record use of concomitant medications (including acetaminophen, herbal remedies, and other over-the-counter medications) on the concomitant medications eCRF. • Record alcohol use on the liver event alcohol intake eCRF. 
If ALT $\geq 3xULN$ AND bilirubin $\geq 2xULN$ or INR >1.5:
 
 • Anti-nuclear antibody, anti-smooth muscle antibody, Type 1 anti-liver kidney microsomal antibodies, and quantitative total IgG or gamma globulins. • Serum acetaminophen adduct high performance liquid chromatography (HPLC) assay (quantifies potential acetaminophen contribution to liver injury in participants with definite or likely acetaminophen use in the preceding week [James et al, 2009].) NOTE: Not required in China. • Liver imaging (ultrasound, magnetic resonance, or computerized tomography) and/or liver biopsy to
--	--

	evaluate liver disease; complete liver imaging and/or liver biopsy eCRFs.
--	---

- ^a Serum bilirubin fractionation should be performed if testing is available. If serum bilirubin fractionation testing is unavailable, record the absence/presence of detectable urinary bilirubin on dipstick, which is indicative of direct bilirubin elevations suggesting liver injury.
- ^b All events of ALT $\geq 3 \times \text{ULN}$ and bilirubin $\geq 2 \times \text{ULN}$ ($>35\%$ direct bilirubin) or ALT $\geq 3 \times \text{ULN}$ and INR >1.5 may indicate severe liver injury (possible 'Hy's Law') and must be reported as an SAE (excluding studies of hepatic impairment or cirrhosis). The INR measurement is not required, and the stated threshold value will not apply to participants receiving anticoagulants.
- ^c Hepatitis A immunoglobulin M (IgM) antibody; HBsAg and HCV-Ab; hepatitis C RNA; cytomegalovirus IgM antibody; Epstein-Barr viral capsid antigen IgM antibody (or if unavailable, heterophile antibody or monospot testing); and hepatitis E IgM antibody.

This document cannot be used to support any marketing authorization application and any extensions or variations thereof.

REDACTED COPY

10.7 Appendix 7: Medical device incidents – definition and procedures for recording, evaluating, follow-up, and reporting

Not applicable.

This document cannot be used to support any marketing authorization application and any extensions or variations thereof.

REDACTED COPY

